10.6. Appendix 6: Kidney Safety Monitoring Guidelines

10.6.1. Laboratory Assessment of Change in Kidney Function and Detection of Kidney Injury

Standard kidney safety monitoring requires assessment of baseline and postbaseline serum creatinine (Scr measurement to eGFR [Scr-based eGFR] or [eCrCl]). Baseline and postbaseline Scys makes it feasible to distinguish AKI from other causes of Scr increase. If Scr increase is confirmed after baseline, then reflex measurement of Scys is indicated to estimate the combined Scr-Scys eGFR calculation (for adults only).

Regardless of whether kidney function monitoring tests are required as a routine safety monitoring procedure in the study, if the investigator or sponsor deems it necessary to further assess kidney safety and quantify kidney function, then these test results should be managed and followed per standard of care.

10.6.2. Age-Specific Kidney Function Calculation Recommendations

10.6.2.1. Adults (18 Years and Above)—2021 CKD-EPI Equations

•			-
2021 CKD-EPI	Ser	Seys	Recommended eGFR Equation
Scr Only	(mg/dL)	(mg/L)	
Female	if ≤ 0.7	N/A	eGFR = 143 × (Scr/0.7) ^{-0.241} × (0.9938) ^{Ago}
Female	if > 0.7	N/A	eGFR = 143 × (Scr/0.7) ^{-1.200} × (0.9938) ^{Ago}
Male	if ≤ 0.9	N/A	eGFR = 142 × (Scr/0.9) ^{-0.302} × (0.9938) ^{Ago}
Male	if > 0.9	N/A	eGFR = 142 × (Scr/0.9) ^{-1.200} × (0.9938) ^{Ago}
2021 CKD-EPI	Scr	Sevs	Recommended eGFR Equation
Scr-Scys Combined	(mg/dL)	(mg/L)	
			$eGFR = 130 \times (Scr/0.7)^{-0.219} \times (Scys/0.8)^{-0.323} \times (0.9961)^{Ago}$
Female	if ≤ 0.7	$if \le 0.8$	eGFR = 130 × (Scf/0.7) **** × (Scys/0.8) **** × (0.9901)***
Female	if ≤ 0.7	if > 0.8	eGFR = 130 × (Scr/0.7) ^{-0.219} × (Scys/0.8) ^{-0.778} × (0.9961) ^{Age}
Female	if > 0.7	if ≤ 0.8	eGFR = 130 × (Scr/0.7) ^{-0.544} × (Scys/0.8) ^{-0.323} × (0.9961) ^{Ago}
Female	if > 0.7	if > 0.8	eGFR = 130 × (Scr/0.7) ^{-0.544} × (Scys/0.8) ^{-0.778} × (0.9961) ^{Ago}
Male	if ≤ 0.9	if ≤ 0.8	eGFR = 135 × (Scr/0.9) ^{-0.144} × (Scys/0.8) ^{-0.323} × (0.9961) ^{Ago}
Male	if ≤ 0.9	if > 0.8	eGFR = 135 × (Scr/0.9) ^{-0.144} × (Scys/0.8) ^{-0.778} × (0.9961) ^{Age}
Male	if > 0.9	if ≤ 0.8	eGFR = 135 × (Scr/0.9) ^{-0.544} × (Scys/0.8) ^{-0.323} × (0.9961) ^{Ago}
Male	if > 0.9	if > 0.8	eGFR = 135 × (Scr/0.9) ^{-0.544} × (Scys/0.8) ^{-0.778} × (0.9961) ^{Ago}
			1

Inker LA et al. N Engl J Med. 2021;385:1737-49.

10.6.3. Adverse Event Grading for Kidney Safety Laboratory Abnormalities

AE grading for decline in kidney function (ie, eGFR or eCrCl) will be according to KDIGO criteria.

10.7. Appendix 7: ECG Findings of Potential Clinical Concern

ECG Findings That May Qualify as AEs

- Marked sinus bradycardia (rate <40 bpm) lasting minutes.
- New PR interval prolongation >280 ms.
- New prolongation of QTcF to >480 ms (absolute).
- New-onset atrial flutter or fibrillation, with controlled ventricular response rate: ie, rate <120 bpm.
- New-onset type I second-degree (Wenckebach) AV block of >30 seconds' duration.
- Frequent PVCs, triplets, or short intervals (<30 seconds) of consecutive ventricular complexes.

ECG Findings That May Qualify as SAEs

- QTcF prolongation >500 ms.
- New ST-T changes suggestive of myocardial ischemia.
- New-onset LBBB (QRS complex >120 ms).
- New-onset right bundle branch block (QRS complex >120 ms).
- Symptomatic bradycardia.
- Asystole:
 - In awake, symptom-free participants in sinus rhythm, with documented periods
 of asystole ≥3.0 seconds or any escape rate <40 bpm, or with an escape rhythm
 that is below the AV node;
 - In awake, symptom-free participants with atrial fibrillation and bradycardia with 1 or more pauses of at least 5 seconds or longer;
 - Atrial flutter or fibrillation, with rapid ventricular response rate: rapid = rate
 >120 bpm.
- Sustained supraventricular tachycardia (rate >120 bpm) ("sustained" = short duration with relevant symptoms or lasting >1 minute).
- Ventricular rhythms >30 seconds' duration, including idioventricular rhythm (HR <40 bpm), accelerated idioventricular rhythm (HR 40 bpm to <100 bpm), and monomorphic/polymorphic ventricular tachycardia (HR >100 bpm [such as torsades de pointes]).
- Type II second-degree (Mobitz II) AV block.
- Complete (third-degree) heart block.

ECG Findings That Qualify as SAEs

- Change in pattern suggestive of new myocardial infarction.
- Sustained ventricular tachyarrhythmias (>30 seconds' duration).
- Second- or third-degree AV block requiring pacemaker placement.
- Asystolic pauses requiring pacemaker placement.
- Atrial flutter or fibrillation with rapid ventricular response requiring cardioversion.
- Ventricular fibrillation/flutter.
- At the discretion of the investigator, any arrhythmia classified as an adverse experience.

The enumerated list of major events of potential clinical concern are recommended as "alerts" or notifications from the core ECG laboratory to the investigator and Pfizer study team, and not to be considered as all-inclusive of what to be reported as AEs/SAEs.

10.8. Appendix 8: AEs, ADEs, SAEs, SADEs, USADEs, and Device Deficiencies: Definitions and Procedures for Recording, Evaluating, Follow-Up, and Reporting in Medical Device Studies

Definitions of a Medical Device Deficiency

The definitions and procedures detailed in this appendix are in accordance with ISO 14155 and the European MDR 2017/745 for clinical device research (if applicable).

Both the investigator and the sponsor will comply with all local reporting requirements for medical devices.

The detection and documentation procedures described in this protocol apply to all sponsor medical devices provided for use in the study (see Section 6.2.2) for the list of sponsor medical devices).

10.8.1. Definition of AE and ADE

AE and ADE Definition

- An AE is defined in Appendix 3 (Section 10.3.1).
- An ADE is defined as an AE related to the use of an investigational medical device.
 This definition includes any AEs resulting from insufficient or inadequate instructions
 for use, deployment, implantation, installation, or operation, or any malfunction of the
 investigational medical device as well as any event resulting from use error or from
 intentional misuse of the investigational medical device.

10.8.2. Definition of SAE, SADE, and USADE

SAE Definition

An SAE is defined in Appendix 3 (Section 10.3.2).

SADE Definition

- An SADE is defined as an ADE that has resulted in any of the consequences characteristic of an SAE.
- Any device deficiency that might have led to an SAE if appropriate action had not been taken, intervention had not occurred, or circumstances had been less fortunate.

USADE Definition

A USADE (also identified as UADE in US Regulations 21 CFR 813.3) is a SADE that
by its nature, incidence, severity, or outcome has not been identified in the current
version of the risk analysis management file.

10.8.3. Definition of Device Deficiency

Device Deficiency Definition

 A device deficiency is an inadequacy of a medical device with respect to its identity, quality, durability, reliability, safety, or performance. Device deficiencies include malfunctions, use errors, and inadequate information supplied by the manufacturer.

10.8.4. Recording/Reporting and Follow-Up of Medical Device Deficiencies

Device Deficiency Recording

- When a device deficiency occurs, it is the responsibility of the unblinded site staff to review all documentation (eg, hospital progress notes, laboratory reports, and diagnostic reports) related to the event.
- The unblinded site staff will then record all relevant device deficiency information in the participant's medical records, in accordance with the investigator's normal clinical practice, and will also capture the required information on the Medical Device Complaint form.
- It is not acceptable for the unblinded site staff to send photocopies of the participant's medical records to Pfizer Safety in lieu of following the reporting process described in the Medical Device Complaint form.
- There may be instances when copies of medical records for certain cases are requested by Pfizer Safety. In this case, all participant identifiers, with the exception of the participant number, will be redacted on the copies of the medical records before submission to Pfizer Safety.
- If the unblinded site staff determines that the medical device deficiency may have injured the participant (ie, the medical device deficiency is associated with an AE or SAE), then the unblinded site staff will attempt to establish a diagnosis of the event based on signs, symptoms, and/or other clinical information. Whenever possible, the diagnosis will be documented in the participant's medical record and recorded as the AE or SAE rather than the individual signs/symptoms. Requirements for recording and reporting an AE or SAE are provided in Appendix 3 (Section 10.3.3).
- For device deficiencies, it is very important that the unblinded site staff describes any
 corrective or remedial actions taken to prevent recurrence of the incident.
- A remedial action is any action other than routine maintenance or servicing of a medical device where such action is necessary to prevent recurrence of a device deficiency. This includes any amendment to the device design to prevent recurrence.

Assessment of Causality Occurring in Conjunction With a Medical Device Deficiency

- If an AE or SAE has occurred in conjunction with a medical device deficiency, the
 investigator must assess the relationship between each occurrence of the AE or SAE
 and the medical device deficiency. The investigator will use clinical judgment to
 determine the relationship.
- A "reasonable possibility" of a relationship conveys that there are facts, evidence, and/or arguments to suggest a causal relationship, rather than a relationship cannot be ruled out.
- Alternative causes, such as underlying disease(s), concomitant therapy, and other risk factors, as well as the temporal relationship of the event to study intervention administration will be considered and investigated.
- The investigator will also consult the IB in their assessment.
- For each device deficiency, the investigator must document in the medical notes that they have reviewed the device deficiency and have provided an assessment of causality.
- There may be situations in which an SAE has occurred and the investigator has
 minimal information to include in the initial report to the sponsor. However, it is very
 important that the investigator always make an assessment of causality for every event
 before the initial transmission of the SAE data to the sponsor.
- The investigator may change their opinion of causality in light of follow-up information and send an SAE follow-up report with the updated causality assessment.
- The causality assessment is one of the criteria used when determining regulatory reporting requirements.

Follow-Up of Medical Device Deficiency

- The investigator is obligated to perform or arrange for the conduct of supplemental
 measurements and/or evaluations, as medically indicated or as requested by the
 sponsor to elucidate the nature and/or causality of the device deficiency as fully as
 possible. This may include additional laboratory tests or investigations,
 histopathological examinations, or consultation with other healthcare providers.
- New or updated information regarding the nature of the device deficiency will be recorded in the originally completed Medical Device Complaint form.
- New or updated information regarding any SAE that was potentially associated with the medical device deficiency will be submitted to Pfizer Safety on the Vaccine SAE Reporting Form within 24 hours of receipt of the information, according to the requirements provided in Section 10.3.

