6.2.2. Medical Devices

In this study, the PFS and vial adapter required for the preparation of RSVpreF are considered medical devices. For Substudy A and Substudy B (1.0-mL formulation), RSVpreF will be provided in a kit that contains a vial of RSVpreF lyophilized powder, a PFS containing sterile water, and a vial adapter. Instructions for their use are provided in the IPM.

All medical device deficiencies (including malfunction, use error, and inadequate labeling) shall be documented and reported by the investigator throughout the clinical investigation (see Section 8.4.9) and appropriately managed by the sponsor.

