8.4.9. Medical Device Deficiencies

Medical devices being provided for use in this study are those listed in Section 6.2.2. In order to fulfill regulatory reporting obligations worldwide, the unblinded site staff is responsible for the detection and documentation of events meeting the definitions of device deficiency that occur during the study with such devices.

The definition of a medical device deficiency can be found in Section 10.8.3.

Note: AEs and/or SAEs that are associated with a medical device deficiency will follow the same processes as other AEs or SAEs, as outlined in Sections 8.4.1 to 8.4.4 and Section 10.3 of the protocol.

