10.9.8.2.2. Blinding of Site Personnel

The study staff receiving, storing, dispensing, preparing, and administering the study interventions will be unblinded. All other study and site personnel, including the investigator and investigator staff, will be blinded to assignment of study intervention. In particular, the individuals who evaluate participant safety will be blinded. Because there are differences in physical appearance between study interventions, study interventions will be administered in a manner that prevents the participants from identifying the study intervention based on its appearance.

The PI will assign the responsibility of the unblinded dispensers/administrators to persons who will not participate in the evaluation of any study participant. To ensure adequate coverage, at least 2 unblinded dispensers/administrators will be assigned per site. Members of the study site nursing/medical staff or clinic pharmacy will fulfill these roles. Contact between the unblinded dispensers and study participants should be kept to a minimum.

The investigator, study coordinator, and any site staff other than the unblinded dispensers/administrators must not be allowed to know the study intervention assigned to any study participant and must not be allowed to see the study intervention container contents.

In the event of a Quality Assurance audit, the auditor(s) will be allowed access to unblinded study intervention records at the site(s) to verify that randomization/dispensing has been done accurately.

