10.10.8.2.2. Blinding of Site Personnel

The study staff receiving, storing, dispensing, preparing, and administering the study interventions will be unblinded. All other study and site personnel, including the investigator and investigator staff, will be blinded to assignment of study intervention. In particular, the individuals who evaluate participant safety will be blinded. Because the administered volume and appearance differ between study interventions, study interventions will be administered in a manner that prevents the participants from identifying the study intervention based on these factors.

The PI will assign the responsibility of the unblinded dispensers/administrators to persons who will not participate in the evaluation of any study participant. To ensure adequate coverage, at least 2 unblinded dispensers/administrators will be assigned per site. Members of the study site nursing/medical staff or clinic pharmacy will fulfill these roles. Contact between the unblinded dispensers and study participants should be kept to a minimum. The investigator, study coordinator, and any site staff other than the unblinded dispensers/administrators must not be allowed to know the study intervention assigned to any study participant and must not be allowed to see the study intervention container contents.

In the event of a Quality Assurance audit, the auditor(s) will be allowed access to unblinded study intervention records at the site(s) to verify that randomization/dispensing has been done accurately.

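### Device-deficiency duties placed on the blinded investigator (Protocol 6.2.2, 10.8.4, 10.8.6) conflict with Section 8.4.9 and with the blinding rules

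*Protocol*

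**What the plan says.** **Devices.** Protocol Section 6.2.2 names two devices, the prefilled syringe and the vial adapter used to prepare RSVpreF, and Section 8.4.9 limits the device list to these. Section 6.2.2 states: "For Substudy A and Substudy B (1.0-mL formulation), RSVpreF will be provided in a kit that contains a vial of RSVpreF lyophilized powder", together with the sterile-water syringe and the adapter.

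**Who handles deficiencies.** Section 6.2.2 says that they "shall be documented and reported by the investigator throughout the clinical investigation". Section 8.4.9 says that "the unblinded site staff is responsible for the detection and documentation of events meeting the definitions of device deficiency", and 8.4.9.2 to 8.4.9.4 extend this to follow-up and reporting. Section 10.8.4 begins in line with 8.4.9, with unblinded staff entering the details in the participant's medical records and on the complaint form. It then turns to the investigator, who must note for each deficiency that "they have reviewed the device deficiency and have provided an assessment of causality" and who also carries the follow-up. In Section 10.8.6 the 24-hour reporting clock starts when the investigator decides that the event is a device deficiency.

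**Blinding.** After listing the unblinded dispensing and administering staff, Section 10.9.8.2.2 says: "All other study and site personnel, including the investigator and investigator staff, will be blinded to assignment of study intervention". Section 10.10.8.2.2 says the same for Substudy B. Both sections forbid the investigator to learn any participant's assignment, and both give the unblinded roles to "persons who will not participate in the evaluation of any study participant". Section 10.8.4 nevertheless provides that, where a deficiency may have injured a participant, "the unblinded site staff will attempt to establish a diagnosis of the event based on signs, symptoms, and/or other clinical information".

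**The concern.** A device deficiency is evidence about how a dose was prepared. If preparation differs between the two groups at a visit, an investigator who reviews a deficiency for a named participant learns something about allocation. The same person grades AEs and judges whether they are related to study intervention. No masked-review step is described, and no unblinded assessor is named for device causality. Section 6.5.4 covers emergency unblinding, so disclosure through routine device paperwork might never be logged as a broken blind. In the other direction, staff who know the allocation are asked to make a clinical diagnosis that the blinding sections keep from them.

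**Working it through.** The plan states no figure on this point, so the check sets the sections side by side.

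**Step 1: who holds each duty (Protocol).**

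| Duty | Unblinded site staff | Investigator |
|---|---|---|
| Documentation | 8.4.9, 10.8.4 | 6.2.2 |
| Deciding that an event is a deficiency | 8.4.9.3 | 10.8.6 |
| Follow-up | 8.4.9.2 | 10.8.4 |
| Causality | none named | 10.8.4 |

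There is a second route. Section 10.8.4 places deficiency details in the medical records, and Section 10.3.3 has the investigator review all documentation related to an AE. The details would reach the investigator even without the review duty.

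**Step 2: who uses the kit at each visit** (6.2.2, 10.9.6.1, 10.9.8.1, 10.10.8.1).

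| Visit | Kit stated | Kit not stated |
|---|---|---|
| A101 | Combination, 125 | qIRV alone, no reconstitution product, 125 |
| A102 | RSVpreF, 125 | Saline placebo from a vial, 125 |
| B101 | 1.0 mL, 100 | 0.5 mL, cake reconstituted with qIRV suspension, 100 |

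Allocation is 1:1, so before any device information the probability of either group is 0.5. In Substudy A, a deficiency tied to a dosed participant at a known visit moves it to 1: Group 1 at A101, Group 2 at A102. In Substudy B, the sterile-water syringe is not listed for the 0.5-mL arm, so a syringe deficiency points to the 1.0-mL arm. The 0.5-mL preparation text is partly redacted, so use of a vial adapter there cannot be excluded. An adapter deficiency is therefore strongly suggestive, not conclusive.

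**Step 3: where the investigator's judgement counts.** Three of the six stopping criteria in each of 10.9.10.5.1 and 10.10.10.5.1 use investigator relatedness: confirmed abnormal troponin, a Grade 4 unsolicited AE or any SAE, and two or more similar AEs of Grade 3 or higher. One participant is enough for the first two. The ECG, confirmed myocarditis or pericarditis, and death criteria do not use it. The Substudy A rules cover Day 1 to Day 28 after Vaccination 1. Visit A102 falls 28 to 35 days after Vaccination 1, at or beyond the end of that window. The stopping-rule link therefore concerns A101 and B101:

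- planned first doses prepared with the kit: 125 + 100 = 225
- all planned first doses: 250 + 200 = 450
- share: 225 / 450 = 50%

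Outside the stopping rules, the judgement enters the related-AE and severe-AE summaries in SAP 6.1.4.2, which SAP 6.1.6 carries over to Substudy B. Deficiencies at A102 bear on these.

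**The case against.** The best defence is that the duty is narrower than its words. The bullet requiring review sits under a heading on causality arising in conjunction with a deficiency, and the first bullet there opens "If an AE or SAE has occurred in conjunction with a medical device deficiency". Reading it as AE-linked deficiencies only is plausible. That would reduce the number of cases, but the remaining ones are exactly those in which relatedness is being judged, so the conflict stays.

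Four stronger readings are tempting, and the documents do not support them.

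- A reader might infer that every deficiency review unblinds. One found in undispensed stock reveals nothing about any participant.
- A reader might infer that the leak always falls on the same arms. In Substudy A both groups use the kit, at different visits; it is the visit together with the kit that identifies the group.
- A reader might infer that the primary safety results are compromised. The primary AE and SAE percentages count any event regardless of relatedness, related and severe AEs are supplementary summaries, and neither substudy tests a hypothesis. The stopping rules are not comparative: all participants receive active vaccine at Vaccination 1, and sponsor personnel confirm whether a rule is met. The documents do not show in which direction, or how far, knowing the group would move a judgement.
- A reader might multiply the 350 planned kit uses (125 + 125 + 100) by a guessed rate to obtain a head count. No deficiency rate is given, and not every deficiency would be tied to a participant.

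These points limit the consequence. They do not reconcile the sections.

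**Conclusion.** The contradiction stands. As written, the investigator cannot carry out the device duties in 6.2.2, 10.8.4 and 10.8.6 for a dosed participant at a known visit and remain blind as 10.9.8.2.2 and 10.10.8.2.2 require. The exposure is certain in kind for Substudy A and strong, subject to the redacted 0.5-mL text, for Substudy B. Its reach is the investigator's severity and relatedness calls only. Half of the planned first doses are open to it for stopping-rule purposes, but how many would actually be affected cannot be estimated. Separately, asking unblinded staff to diagnose an AE contradicts the rule that they evaluate no participant. Section 8.4.9 shows the intended arrangement; the other sections were not brought into line with it. The point deserves correction because the remedy is cheap and a single related event can trigger a pause.

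**What to change.** Reconcile Protocol Sections 6.2.2, 10.8.4 and 10.8.6 with 8.4.9:

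- Give deficiency determination, documentation, review, follow-up and device causality to unblinded, qualified site staff together with unblinded sponsor clinical staff. Section 10.10.6.1 already names an unblinded study team clinician for Substudy B. Name the equivalent for Substudy A from the unblinded sponsor staff in 10.9.8.2.3.
- Keep deficiency records in the unblinded site file, and remove the instructions to place them in the participant's medical records or notes.
- Leave AE diagnosis, severity and causality to study intervention with the blinded investigator, and delete the instruction that unblinded staff establish the AE diagnosis.
- If the investigator must see a deficiency for safety reasons, log it as an unblinding under 6.5.4.

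The cost is protocol wording, one extra hand-off when a deficiency coincides with an AE, and a check that the reallocation still meets the device standards cited at the start of Section 10.8.
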